#### 4.7 Schedule of events

**Table 1. Schedule of Events for Group A and Treatment Group**

	Screening	Baseline / Treatment 1	Treatment 2 (Optional) b	Treatment 3 (Optional) b	Treatment 4 (Optional) b	Follow-up	Follow-up	Final visit / Early termination
	D-21 to D1	D1	5W( $\pm 1w$ ) after treatment 1	5W( $\pm 1w$ ) after treatment 2	5W( $\pm 1w$ ) after treatment 3	5W( $\pm 1w$ ) after Last treatment	6M ( $\pm 2w$ ), 9M ( $\pm 2w$ ), 12M ( $\pm 2w$ ), and 18M ( $\pm 3w$ ) after Baseline	24M ( $\pm 4w$ ) after Baseline
Informed consent	X							
Demography	X							
Height		X						
Weight		X					X	X
Medical history & concurrent diseases	X	X a						
Concomitant medication/procedures	X	X a	X	X	X	X	X	X
Vital signs		X c						
Laboratory tests	X						X d	X e
Pregnancy test for childbearing potential women	X	X a,c	X c	X c	X c			X
Inclusion and Exclusion criteria	X	X a						
Randomization		X						

Treatment		X	X	X	X			
MMVS (Blinded Evaluator)	X	X a,c					X	X
MMVS (treating investigator)	X	X a,c	X c	X c	X c	X	X	X
Photography		X c	X c	X c	X c	X	X	X
GAIS (Treating investigator and Subject)			X c	X c	X c	X	X	X
Subject satisfaction questionnaire							X	X
Dispense subject diary		X	X	X	X			
Review and collect subject diary			X	X	X	X		
Device deficiencies		X	X	X	X			
Assessment of AE	X	X a	X	X	X	X	X	X
Study termination								X

- a) Omitted if screening and baseline visit occur on the same day.
- b) The visit is omitted if optional treatment was not performed.
- c) Performed prior to treatment.
- d) Only performed at 12M.
- e) Only performed at early termination if termination occurs before 12M visit.

	
Title 43CHSA1803 Clinical Study Protocol
	
Doc id MA-39381

--	--	-----------------------------------

**Table 2. Schedule of Events for Control Group**

	Screening	Baseline	Follow-up	Final visit / Early termination
	D-21 to D1	D1	6M( $\pm 2w$ ) and 9M ( $\pm 2w$ ) after Baseline	12M ( $\pm 2w$ ) after Baseline
Informed consent	X			
Demography	X			
Height		X		
Weight		X	X	X
Medical history & concurrent diseases	X	X a		
Concomitant medication/procedures	X	X a	X	X
Vital signs		X		
Laboratory tests	X			
Pregnancy test for childbearing potential women	X			
Inclusion and Exclusion criteria	X	X a		
Randomization		X		
MMVS (Blinded Evaluator)	X	X a	X	X
MMVS (treating investigator)	X	X a	X	X
Photography		X	X	X
GAIS (Treating investigator and Subject)			X	X
Assessment of AE	X	X a	X	X
Study termination				X

a) Omitted if screening visit and baseline visit occur on the same day.

 GALDERMA	Title 43CHSA1803 Clinical Study Protocol	Doc id MA-39381
--	--	---------------------------

## 4.8 Visits

### 4.8.1 Visits for Group A and Treatment Group

#### 4.8.1.1 Screening (D-21 to D1)

- Informed consent
- Demography (Initials, Date of birth, Gender and Ethnic origin)
- Screening laboratory tests (haematology and serum chemistry)
- Inclusion and exclusion criteria
- Pregnancy test for childbearing potential women
- MMVS (by Blinded Evaluator and treating investigator)
- Medical history/concurrent diseases including prior facial dermatological procedures performed, and fillers or implants used
- Concomitant medications/procedures
- AE during the visit

#### 4.8.1.2 Baseline (D1)

- Height and Weight
- Medical history/concurrent diseases
- Vital signs (before treatment, pulse rate, blood pressure, respiratory rate, body temperature)
- Inclusion and exclusion criteria
- Randomization
- Pregnancy test for childbearing potential women (before treatment)
- Photography (before treatment)
- MMVS (before treatment, by Blinded Evaluator and treating investigator)
- Treatment
- Dispense subject diary
- Concomitant medications /procedures
- Device deficiencies
- AE since last visit

If screening and baseline visit occur on the same day, the following procedures for baseline will not be repeated.

- Medical history/concurrent diseases
- Inclusion and exclusion criteria
- MMVS (before treatment, by Blinded Evaluator and treating investigator)
- Concomitant medications /procedures
- Pregnancy test for childbearing potential women(before treatment)
- AE since last visit

#### 4.8.1.3 Optional treatment 2, 3, and 4 (only for subjects who receive the treatment)

- Photography (before treatment)

 GALDERMA	Title 43CHSA1803 Clinical Study Protocol	Doc id MA-39381
--	--	---------------------------

Effective date: 2019-06-20 00:56

- MMVS (before treatment, by treating investigator)
- GAIS (before treatment, by treating investigator and subject)
- Pregnancy test for childbearing potential women (before treatment)
- Treatment
- Collect and review subject diary
- Dispense subject diary
- Concomitant medications/procedures
- Device deficiencies
- AE since last visit

#### *4.8.1.4 5W( $\pm 1w$ ) after last treatment*

- Photography
- MMVS (by treating investigator)
- GAIS (by treating investigator and subject)
- Collect and review subject diary
- Concomitant medications /procedures
- AE since last visit

#### *4.8.1.5 6M ( $\pm 2w$ ), 9M ( $\pm 2w$ ), 12M ( $\pm 2w$ ), and 18M ( $\pm 3w$ ) Follow-up*

- Weight
- Photography
- MMVS (by Blinded Evaluator and treating investigator)
- GAIS (by treating investigator and subject)
- Subject satisfaction questionnaire
- Concomitant medications /procedures
- AE since last visit
- Laboratory tests (Only performed at 12M)

#### *4.8.1.6 24M ( $\pm 4w$ ) Final visit or Early termination*

- Weight
- Photography
- MMVS (by Blinded Evaluator and treating investigator)
- GAIS (by treating investigator and subject)
- Subject satisfaction questionnaire
- Pregnancy test for childbearing potential women
- Concomitant medications/procedures
- AE since last visit
- Laboratory tests (Only performed at early termination if termination occurs before 12 months visit)
- Study termination

*Effective*

Version: 2.0

 GALDERMA	Title 43CHSA1803 Clinical Study Protocol	Doc id MA-39381
--	--	---------------------------

#### 4.8.2 Visits for Control Group

##### 4.8.2.1 *Screening (D-21 to D1)*

- Informed consent
- Demography (Initials, Date of birth, Gender and Ethnic origin)
- Screening laboratory tests (haematology and serum chemistry)
- Inclusion and exclusion criteria
- Pregnancy test for childbearing potential women
- MMVS (by Blinded Evaluator and treating investigator)
- Medical history/concurrent diseases including prior facial dermatological procedures performed, and fillers or implants used
- Concomitant medications/procedures
- AE during the visit

##### 4.8.2.2 *Baseline (D1)*

- Height and Weight
- Medical history/concurrent diseases
- Vital signs (pulse rate, blood pressure, respiratory rate, body temperature)
- Inclusion and exclusion criteria
- Randomization
- Photography
- MMVS (by Blinded Evaluator and treating investigator)
- Concomitant medications /procedures
- AE since last visit

If screening and baseline visit occur on the same day, the following procedures for baseline will not be repeated.

- Medical history/concurrent diseases
- Inclusion and exclusion criteria
- MMVS (by Blinded Evaluator and treating investigator)
- Concomitant medications /procedures
- AE since last visit

##### 4.8.2.3 *6M (±2w), 9M (±2w) Follow-up*

- Weight
- Photography
- MMVS (by Blinded Evaluator and treating investigator)
- GAIS (by treating investigator and subject)
- Concomitant medications /procedures
- AE since last visit

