#### Treatment

Each subject assigned to Group A and Treatment Group will receive up to 4 injection sessions with 5( $\pm 1$ ) weeks (at least 4 weeks) intervals. Initial treatment will be on Day 1. Study treatments should be stopped if optimal midface augmentation has been obtained or a maximum of 4 injection sessions completed. Optimal midface augmentation is defined as the best possible aesthetic result that can be obtained for an individual study participant, as agreed upon by the treating investigator and subject.

Subjects assigned to the Control Group will not receive treatment during the study.

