### 8.2 Laboratory assessment

Laboratory samples for Haematology and Serum chemistry assessment will be taken at the screening visit (day -21 to day 1) for all subjects. In Group A and Treatment Group, it will also be taken at 12 months visit or at early termination if termination occurs before 12 months visit.

The following laboratory assessments will be performed:

- Haematology: haemoglobin, red blood cells, white blood cells, differential count and platelet count.
- Serum chemistry: renal function tests (creatinine and BUN); and liver function tests (aspartate amino transferase (ASAT), alanine amino transferase (ALAT) total bilirubin, direct bilirubin and indirect bilirubin).

Pregnancy test (Urine HCG) will be performed at screening, all injection visits (prior to treatment and the study completion/early termination for Group A and Treatment Group, and at screening for Control group, in all women of childbearing potential, including those currently using contraception. The test result must be negative for the subject to receive any treatment with study product.

Other laboratory test might be performed at the discretion of the investigator. All laboratory assays will be performed at a local laboratory. Reference ranges will be supplied by the

 GALDERMA	Title 43CHSA1803 Clinical Study Protocol	Doc id MA-39381
--	--	---------------------------

Effective date: 2019-06-20 00:56

Effective

Version: 2.0

laboratory and used by the Investigator to assess the laboratory data for clinical significance and out of range pathological changes.

The results of the hematology and serum chemistry will only be used for safety assessment by investigator and will not be collected in the eCRF. The pregnancy test for women of childbearing potential will be recorded in the eCRF.

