### 8.3 Adverse Events

#### 8.3.1 Definition of Adverse Events

An AE is any untoward medical occurrence, unintended disease or injury, or untoward clinical signs (including abnormal laboratory findings) in subjects, users or other persons\*, whether or not related to the study product.

This definition includes:

- events related to the investigational product or the reference product
- events related to the procedures involved

\*For users or other persons, this definition is restricted to events related to the investigational product

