#### 8.3.3 Recording Instructions

AE will begin to be collected after ICF signed. Each subject will be questioned about AEs at each clinical visit following the screening visit. The question asked will be "Since your last clinical visit have you had any health problems?" Information on AEs can also be obtained from signs and symptoms detected during each examination or from a laboratory test,

	
Title 43CHSA1803 Clinical Study Protocol
	
Doc id MA-39381

--	---	----------------------------

2019-06-20 00:56

Effective date:

Effective

Version: 2.0

observations by the study personnel, subject diaries or spontaneous reports from the subjects.

The Investigator will assess the presence of any papules (<5mm in diameter) or nodules (≥5mm in diameter). If present, the papules/nodules will be recorded as AE and should be further assessed as visible/non-visible and inflammatory/non-inflammatory.

When an AE is related to a device deficiency (refer to section 8.4), including technical device malfunction, the AE shall be recorded on the AE module in the eCRF and the technical complaint shall be reported separately on the clinical study complaint form.

Investigators, or other study personnel, will record all AEs in the eCRF, including:

- Event term (recorded in standard medical terminology and avoiding abbreviations),
- Description of event and affected area (if applicable),
- Start date (First day with symptoms)
- Stop date (Last day with symptoms)
- Intensity (mild, moderate or severe according to definition in section 8.3.3.1)
- Seriousness (serious or not serious, according to definition in section 8.3.2)
- Causal relationship to study product and study product injection procedure (yes or no)
- Action taken (none, medication treatment, non-pharmacological treatment or other procedures/ tests, subject withdrawn)
- Outcome of the AE (ongoing, recovered, recovered with sequelae, death, chronic/ stable, not recovered at study end)

The AE module in the eCRF must be signed and dated by the Investigator.

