		n (%)	Serial Puncture	

2019-10-24 08:59

Effective date:

Effective

Version: 1.0

Characteristic	Visit	Statistic	Answer	Result
		n (%)	Fanning	
		n (%)	Other	
	Treatment 4 (optional)	n (%)	Linear Retrograde	
		n (%)	Serial Puncture	
		n (%)	Fanning	
		n (%)	Other	
Post-treatment care (ice and massage) according to study protocol?	Baseline / Treatment 1	n (%)	Yes	
		n (%)	No	
	Treatment 2 (optional)	n (%)	Yes	
		n (%)	No	
	Treatment 3 (optional)	n (%)	Yes	
		n (%)	No	
	Treatment 4 (optional)	n (%)	Yes	
		n (%)	No	
Any deviation from the treatment procedure as described in the study protocol?	Baseline / Treatment 1	n (%)	Yes	
		n (%)	No	
	Treatment 2 (optional)	n (%)	Yes	
		n (%)	No	
	Treatment 3 (optional)	n (%)	Yes	
		n (%)	No	
	Treatment 4 (optional)	n (%)	Yes	
		n (%)	No	

List deviations:...

2019-10-24 08:59

Effective date:

Effective

Version: 1.0

Safety**Table 3-42: Anticipated injection related reactions recorded in the subject diary after first treatment (both sides of the face combined), Safety population**

Event	Treatment with Sculptra N=XX							
	Subjects		Maximum intensity					
			Mild		Moderate		Severe	
	n	%	n	%	n	%	n	%
Pain								
Tenderness								
Localized redness								
Bruising								
Hematoma								
Edema								
Other								
No diary events								

 $\% = (n/N)*100$

Note: Percentages for intensity categories are based on the number of subjects reporting the symptom.

Table 3-43: Number of days anticipated injection related reactions recorded in subject diary after first treatment (both sides of the face combined), Safety population

Event	Treatment with Sculptra N=XX					
	n	Mean	SD	Minimum	Median	Maximum
Pain						
Tenderness						
Localized redness						
Bruising						
Hematoma						
Edema						
Other						

Figure 3-5: Proportion of subjects with observed anticipated injection related reactions (to any intensity level) after first treatment with Sculptra (both sides of the face combined), Safety population

Same tables and figure for treatment sessions two, three and four

 GALDERMA	Title 43CHSA1803 Statistical Analysis Plan - Sculptra China	Doc id MA-40407
--	---	---------------------------

Effective date: 2019-10-24 08:59

Table 3-44: Brief summary of all AEs, Main study, Safety population

	Sculptra, N=XX			Control, N=YY		
	Subjects		Events	Subjects		Events
	n	%	#	n	%	#
Adverse Events reported, total						
Total, serious						
Total, non-serious						
AEs related to injection procedure and/or product, total						

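### Scheduled adverse-event enquiry is denser in Sculptra than in Control before Month 6, yet SAP Table 3-44 sets crude 12-month rates side by side with no like-for-like period

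*Protocol*

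**What the plan says.** Protocol 8.3.3 ties AE enquiry to visits: "Each subject will be questioned about AEs at each clinical visit following the screening visit". The question covers the time since the previous visit. Diaries, laboratory tests and spontaneous reports are further named sources.

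- **Sculptra.** Subjects "will receive up to 4 injection sessions" (protocol 4.1). AE enquiry is listed for each optional session in 4.8.1.3, whose heading begins "Optional treatment 2, 3, and 4 (only for subjects who receive the treatment". It is listed again 5 weeks after the last treatment (4.8.1.4) and at Months 6, 9 and 12. A footnote to Table 1 adds: "The visit is omitted if optional treatment was not performed". A 4-week diary follows every session.
- **Control.** After baseline, the visits are those under "6M (±2w), 9M (±2w) Follow-up" (4.8.2.3) and Month 12 (4.8.2.4). There is no diary.
- **Laboratory tests.** All subjects are tested at screening. Protocol 8.2 continues: "In Group A and Treatment Group, it will also be taken at 12 months visit", or at early termination before that visit. Protocol 8.3.1 counts as AEs "untoward clinical signs (including abnormal laboratory findings) in subjects". Haematology and chemistry results are not entered in the eCRF.
- **Analysis.** SAP 2.5.3 plans "Table 3-44: Brief summary of all AEs, Main study, Safety population", with subjects, percentages and events for Sculptra and Control in adjacent columns. Tables 3-50 and 3-51 give unrelated AEs for the two arms in the same layout, one table per arm.

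Neither document mentions that the two schedules differ.

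**The concern.** With no active comparator, the Control arm is the only randomised background against which Sculptra's AE rate can be read. If one arm is asked every five weeks or so during the first half-year and the other is asked once at the end of it, short or mild events are more likely to be recalled and recorded in the first. Unrelated AEs, which randomisation should make similar, could then look commoner with Sculptra. The confusion works both ways: the device may look worse than it is, or a true imbalance may be put down to the extra visits. Table 3-44 as planned gives no means of telling these apart.

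**Working it through.** The documents state no figure on this point, so there is none to reproduce. The check is a count from the schedules, followed by an illustration on assumed inputs.

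**1. Scheduled enquiries after baseline** (protocol Tables 1 and 2, section 4.8). With k sessions, a Sculptra subject has k − 1 optional-treatment visits and one visit 5 weeks after the last treatment, so k enquiries before Month 6. Months 6, 9 and 12 add 3.

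| | Before Month 6 | Total to Month 12 |
|---|---|---|
| Sculptra, 1 session | 1 | 4 |
| Sculptra, 2 sessions | 2 | 5 |
| Sculptra, 3 sessions | 3 | 6 |
| Sculptra, 4 sessions | 4 | 7 |
| Control | 0 | 3 |

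Scheduled laboratory draws after screening, to Month 12: one in Sculptra, none in Control.

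**2. First recall interval.** Sculptra: 5 ± 1 weeks, so 4 to 6. Control: 6 × 52.18/12 = 26.1 weeks, with a window of ± 2, so about 24 to 28. Four sessions at the longest spacing put the fourth enquiry at 4 × 6 = 24 weeks, still before the nominal Month 6 visit.

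**3. Where the schedules match.** An AE starting after the Month 6 visit is asked about at Months 9 and 12 in both arms. Diaries have ended by then: the latest fourth session is at 3 × 6 = 18 weeks and its diary closes at 18 + 4 = 22 weeks, before the Month 6 window opens at about 24. The scheduled difference that remains is the Month 12 laboratory draw.

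**4. Illustrative size over 12 months.** Assumptions, none of them given in the documents:

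- the same constant true AE rate r in both arms, set so that true 12-month incidence is 20%, 40% or 60%;
- the chance that an event is captured falls as exp(−lag/τ), where lag is the time to the next enquiry and τ runs from 8 to 52 weeks;
- 5-week spacing of sessions.

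An interval of length L contributes captured time τ(1 − exp(−L/τ)), and recorded incidence is 1 − exp(−r × total captured time).

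Worked case, true incidence 40%, τ = 26: r = −ln(0.6)/52.18 = 0.00979 per week.

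- Control, intervals 26.1, 13.0 and 13.0 weeks: captured time 16.5 + 10.3 + 10.3 ≈ 37.0 weeks; recorded incidence 30.4%.
- Sculptra with four sessions, intervals 5, 5, 5, 5, 6.1, 13.0 and 13.0 weeks: captured time 4 × 4.55 + 5.4 + 10.3 + 10.3 ≈ 44.1 weeks; recorded incidence 35.1%.
- Spurious difference: 4.7 points.

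Across the range (Sculptra v Control; differences taken before rounding):

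| True incidence | Four sessions, τ = 52 | Four sessions, τ = 8 | One session, τ = 52 to 8 |
|---|---|---|---|
| 20% | 18.5% v 17.0%: 1.5 | 12.8% v 8.4%: 4.4 | 0.6 to 1.3 |
| 40% | 37.4% v 34.7%: 2.7 | 26.9% v 18.2%: 8.7 | 1.0 to 2.7 |
| 60% | 56.9% v 53.5%: 3.4 | 43.0% v 30.3%: 12.7 | 1.3 to 4.1 |

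With identical enquiry times the difference is zero by construction.

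**The case against.** The strongest reply is that the plan makes no formal safety comparison. SAP 2.5 calls for description only, and Table 3-44 has no difference column, interval or p-value. The detailed related-AE tables (3-45 to 3-49) cover Sculptra alone. Extra visits follow naturally from comparing repeated injections with no treatment, and the expected bias runs against the device. All of this stands, and it keeps the point modest. Adjacent percentages still invite comparison.

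AEs may also be reported spontaneously, by telephone or at extra visits (protocol 8.3.3, 8.3.4). That softens the imbalance, but no such contact is scheduled for Controls before Month 6.

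A reader might infer more than the documents support:

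- *That Controls are not asked at all until Month 6.* Protocol 4.8.2.2 includes an AE enquiry at baseline unless screening falls on the same day. The gap begins after baseline.
- *That laboratory-detected AEs at Month 12 can arise only in Sculptra.* Protocol 8.2 allows other tests at the investigator's discretion in either arm. Only the scheduled tests are one-sided.
- *That a planned check on causality is undermined.* Neither document plans to use unrelated AEs in that way. SAP 1.5 has the Sponsor review causality and classes any disagreement as related.
- *That the excess could approach 18 points.* Over the first six months alone, assuming 0.8 AEs per subject and 90% v 50% reporting, 1 − exp(−0.72) = 51.3% against 1 − exp(−0.40) = 33.0%. But Table 3-44 covers 12 months. Adding an equal second half at 80% reporting gives 1 − exp(−1.36) = 74.3% against 1 − exp(−1.04) = 64.7%, or 9.7 points. Even that applies 90% reporting throughout the first half, whereas sessions 2 to 4 are optional.
- *That the arms should be compared only after Month 6.* That would discard the whole injection period, when acute effects occur, and would tend to flatter the device.

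**Conclusion.** The point holds as one of unequal ascertainment, not unequal time at risk: nominal main-study follow-up is 12 months in both arms. The schedule counts are certain. The likely direction is towards a higher recorded rate in Sculptra, mainly for mild or unrelated AEs. The size is not known. On the assumptions above it is roughly 1 to 13 points over 12 months with four sessions (1.5 to 12.7) and about 0.6 to 4 with one, so a mix of session counts would fall between. The primary effectiveness analysis is untouched. This is a cheap improvement to how a descriptive table reads, not a flaw that threatens the trial's conclusion.

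**What to change.** In SAP 2.5.3, keep the full main-study rows of Table 3-44 and add the same rows split by AE onset:

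- (a) Day 1/randomisation to the Month 6 visit;
- (b) after the Month 6 visit to the Month 12 visit.

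Label (b) as the period with matched scheduled enquiries. Footnote (a) and the total as having unequal enquiry. In (b), also show the counts without AEs in the Investigations system organ class, in both arms, because the scheduled Month 12 laboratory tests are in Sculptra only. This is an approximation: the AE fields listed in protocol 8.3.3 do not record how an event was detected. Do not let (b) replace the full-period or injection-period comparison.

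The cost is one extra table split, with fewer events in (b). AE start dates are already recorded (protocol 8.3.3), SAP 2.5.3 already has rules for incomplete dates, and SAP 2.1 provides for amendment before database lock. Telephone enquiries to Controls at matching times would address the cause, but they change study conduct and need a protocol amendment. They are optional and not part of this recommendation.

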##### 4.8.2.4 *12M (±2w) Follow-up / Final visit or early termination*

- Weight
- Photography

	Title 43CHSA1803 Clinical Study Protocol	Doc id MA-39381
--	--	---------------------------

Effective date: 2019-06-20 00:56

Effective

Version: 2.0

- MMVS (by Blinded Evaluator and treating investigator)
- GAIS (by treating investigator and subject)
- Concomitant medications /procedures
- AE since last visit
- Study termination

